## Adverse events:

- **Maternal adverse events:** We will collect data on maternal adverse events by asking mothers about intercurrent medical events, which will be reviewed by an obstetrician, including any hospitalizations or illnesses. We will also track and report changes in creatinine or other toxicities in women on PrEP.
- **Infant adverse events:** We will collect data on infant adverse events by asking mothers about infant health or intercurrent medical events, which will be reviewed by a pediatrician.
  - Adverse birth outcomes will include infants that were small for gestational age, pre-term births, miscarriage and stillbirths.

Table 1: PrEP-PP cohort measures by participant study month

and breastfeeding in local languages (at each visit)																
Routine ANC and postnatal care, well-baby visit follow-up (as available in standard of care), including rapid HIV testing, pregnancy, and birth outcomes	X	X	X	X	X	X	X		X		X		X			X
Survey to collect: behavioral acceptability, knowledge, and substance use data	X	X	X	X	X	X	X		X		X		X			X
Screening at enrolment for Hepatitis B and creatinine. If HBsAg+ = excluded from study; if creatinine eGFR<60, excluded from study	X															
Laboratory testing for STIs (chlamydia, gonorrhoea) & treatment if positive	X				X		X									
For women on PrEP:																
Laboratory tests of creatinine (if eGFR<60ml/min cannot continue on PrEP)	X			X												X
PrEP pharmacy refills and adherence supportive counseling monthly (for first 3 months on PrEP) then every 2 months for following months	X	X	X		X		X		X		X		X			X
Laboratory testing: renal function, hepatitis B; DBS taken for TDF-DP adherence measures (bi-monthly in participants on PrEP)	X	X	X		X		X		X		X		X			X
In-depth interviews for 30 participants per site (N=60) among 30 PrEP users and 30 non-PrEP users						X										X
Collect study data on: (1) PrEP counseling, (2) PrEP medication when requested, (3) regular appointments, (4) IEC materials, (5) adherence counselling and support by facility, through patient survey at every study visit	X	X	X	X	X	X	X	X	X	X	X	X	X	X	X	X
Vaginal swab for microbiome	X		X*													

\*between 24 and 28 weeks gestational age.

#### Training, quality assurance and supervision:

- 1. Existing DOH staff: We will conduct an on-site half day training for existing counselors, nurses and midwives and Managers in the two study sites on the study protocol to ensure that they understand and support the integration of the study in their facility.**

- a. **Inclusion of interviews for healthcare providers in health facility to understand their knowledge of and attitudes around PrEP:** We seek to interview existing health care providers including nurses, counselors, midwives and managers to understand their knowledge about PrEP, HIV prevention in pregnancy and any attitudes about PrEP that may affect future integration of PrEP and PrEP uptake in the facility. We will interview approximately 35 health care providers from both facilities (Gugulethu and Hannover Park) and have one focus group in those providers in isiXhosa or Afrikaans. We will record, translate and transcribe their responses and analyze the results thematically in order to develop interventions around provider training and support.

2. **Study staff:** We will hire 2 counselors, 2 nurses, 2 coordinators who will receive a 3-day training program and they will be required to complete the entire training course. After completion of the training, the study PI will observe the counselor and nurse completing each step of the intervention with a mock patient. Upon satisfactory completion of observed sessions, the counselors and nurses will be certified to conduct the study intervention and will receive a completion certificate.

3. **Quality assurance** will occur on three levels. Day-to-day monitoring, supervision, and support of counselors will be carried out by the Study Coordinators (from UCT—1 per facility). The Study Coordinator will provide on the job training to ensure that counselors and nurses respect the study protocol. Adherence to the counseling protocol will be established by the Study Coordinator who will sit in on a random subsample of 20% of counseling sessions to ensure that counselors are adhering to study protocols.

#### Sources of data

There are four sources of data/materials for this trial: (1) survey measures; (2) in-depth interview measures in 60 randomly selected women (n=30 who were on PrEP compared with 30 not on PrEP); (3) laboratory measures; and (4) information abstracted from routine care records, including related to PrEP. The collection of data materials will be conducted by a study measurement team comprised of one study coordinator, one study interviewer, and one fieldworker, per site. All procedures for data collection (regardless of source) will be outlined in a study manual of procedures, with individual activities guided by standard operating procedures (e.g., DBS, specimen transport, or questionnaire administration).

#### *Survey measures*

At study measurement visits, questionnaires will be administered to mothers participating in the study. Following standard procedures, the questionnaires will be translated into isiXhosa and Afrikaans and back translated to ensure appropriate phrasing. Questionnaires will include:

- Basic demographic information and obstetric history (enrollment only)
- Partner's HIV status
- Sexual behaviors in the past month and week including # of sex partners, type of sex, and frequency of sex and condom use
- Substance use information using the AUDIT-C and DAUDIT scales
- Risk perception scales
- Partner, community and social support for PrEP
- For PrEP users, questions related to PrEP adherence according to self-report (the 3-day and 1-month recall and a visual analog scale) and pharmacy-based pill counts will be conducted at each study measurement visit.

- Additional schedules will be used to collect data on symptoms in mothers that are potential side-effects of PrEP use (at all study visits)
- We will also use short questionnaires to collect data on all women's experiences in the study, and the acceptability of the PrEP initiation, including what kind of services were offered at each visit (e.g. counseling, peer mentorship, and IEC materials, medication)
- Self-reported symptoms related to STIs
- This will focus on the positive and negative aspects of their experiences of PrEP initiation in pregnancy and breastfeeding and any factors associated with PrEP initiation, retention, and adherence.

#### *Interview measures*

In addition, a subgroup of 60 randomly selected women participating in the study will be enrolled into a qualitative sub-study to complete one in-depth interview (telephonically during the COVID-19 lockdown) at the end of their study participation. We will randomly select 30 women per site to examine in more detail the acceptability of PrEP, barriers, and facilitators to PrEP adherence over time. We will randomly select 15 women per site who were on PrEP and 15 women not on PrEP. This type of 'process evaluation' information can play a critical role in interpreting the quantitative findings and understanding of how to generalize the intervention to other populations. We plan to conduct interviews after approximately 3 months of PrEP use, so at the first postpartum visit, and then at the end of the study. This sub-study will have a separate informed consent process, although these interviews will be timed to take place immediately after study visits scheduled for the trial.

#### **Updated in-depth interview data collection:**

During the COVID-19 lockdown, we will conduct in-depth interviews over the phone with participants who are willing to be on a call and conduct their interview telephonically. The interviewer will be in a private room and will ask the participant to be in a private, quiet space. The interviewer is an experienced isiXhosa -speaking research assistant and interviews will be digitally recorded over the phone (or in person, after the COVID-19 epidemic lockdown) for later transcription and translation. Updated processes include:

- **Calling participants to assess if they have time conduct an interview (and schedule a time when they can be alone in a quiet place for up to 1 hour)**
- **Recording interviews on the phone (with 2 devices)**
- **Confirm that it is the participant who they are speaking with by confirming their participant ID and date of birth prior to initiating interview**

The interviewer will use a simple question guide to help ensure that key topics are investigated. Interview recordings will collect participant study ID numbers but will not record participant names in any form. Key constructs to be investigated during these interviews include:

- Experiences of study participation, including experiences with study staff, counselors, and clinicians
- Experiences of PrEP initiation and any side effects
- Individual, partner, and family experiences that could be facilitators or barriers to PrEP

#### **Additional survey on long-acting PrEP attitudes and perspectives**

We will recruit a sample of n=300 pregnant and breastfeeding women during their study visits to complete a brief 10 minute survey about their perspectives about potential acceptability of long-acting PrEP options including vaginal rings, injectables or long-acting pills to understand the potential for further research on long-acting PrEP in this population.

## **6. Analytic Considerations**

### Sample size considerations

The projected sample size for the study is 1200 women enrolled from 1st ANC visit until 12-months postpartum (estimated mean of 18-months follow-up). This estimate is based on the following assumptions:

- (1) 60% of women will initiate PrEP during the study period (versus approximately 40% who will not);**
- (2) Approximately 75% of women on PrEP will be retained in care at 12-months (defined as not missing >1 study visit among women on PrEP)**
- (3) 70% of those retained in care (n=378) will adhere to PrEP during at-risk periods.**

A sample size of 1200 women yields 80% power to detect identify a relative risk of 2.0 or greater in key covariates including age (<25 vs.  $\geq$ 25 years), pregnancy and relationship status associated with PrEP initiation versus non-initiation. A sample size of 378 women (e.g. 70% of women retained in the study on PrEP will be adherent as measured by TDF-DP measures) yields 80% power to detect relative risks of 2.0 or greater associated with adherence in the cohort. The analysis will be based on women who complete the 12-month postpartum cohort follow up. We will use relative risk ratios performed at a two-sided  $\alpha$  level of 0.05.

### Statistical analysis considerations

The primary analysis for Aim 1 will focus on measuring the distribution of women across the PrEP cascade including: initiation, retention and adherence. PrEP initiation will be based on a woman's uptake of PrEP and allow for stoppage and re-initiation; PrEP retention **will be defined as not missing >1 visit among those on PrEP (with separate analyses of PrEP stoppage)**. For PrEP adherence for women on PrEP we will measure both perfect adherence (i.e. level of objective adherence throughout pregnancy and breastfeeding periods) as well as "prevention-effective" adherence (i.e. adherence during times of sexual activity) in participants through objective and subjective measures to evaluate agreement between the two measures, and the level of under- or over-reporting. Primary adherence analyses will use objective measures (TDF-DP from DBS) taken on all those who enrolled and initiated PrEP; subsidiary analyses will consider (i) other adherence measures and (ii) multiple imputation for missing adherence data.

- **Use of PrEP will be measured** through alternate definitions of the main outcomes (e.g. adherence by self-report versus adherence by pharmacy refill), compared using measures of agreement and will be analyzed as independent models to contrast estimated associations.
- **Measurement of prevention-effective execution:** Execution refers to PrEP adherence during a time when at-risk sex happens. It is calculated by: number of doses reported, or recorded/number of expected doses based on HIV risk and PrEP initiation/discontinuation
- **Prevention-effective continuation:** Prevention-effective continuation describes the duration of PrEP use during periods of HIV risk and references the absolute time of use during pregnancy and breastfeeding periods. We will adapt the methodology from previous PrEP studies in SA including FEM-PrEP to create a semi-ordinal composite adherence score from blood specimens from DBS every 2-months.

Table 2: Study measures for PrEP-PP

Primary Outcomes	Measurement	Source	Frequency
------------------	-------------	--------	-----------

PrEP initiation	# of women who initiate PrEP over time / total # of women in active cohort = proportion of women who initiate PrEP	Electronic provider log (REDCap)	Daily entry, weekly analysis
PrEP retention	# of women on PrEP who return for study visits (do not miss more than 1 visit) / total # of women in active cohort who are prescribed PrEP= proportion of women on PrEP who are retained in PrEP study	Electronic provider log (REDCap)	Daily, analysis weekly
PrEP adherence-subjective	# of women taking PrEP, who self-report taking their medication daily (& pill count to confirm this) during periods of sexual risk over time / total woman-time on PrEP in active cohort = PrEP adherence rate (subjective)	Electronic provider log (REDCap)	Daily, analysis weekly
PrEP adherence-objective	# of women taking PrEP who have >80% levels at >40ng/mL TDF-DP (indicating dosing in past 24 hours) at 3 rd trimester, delivery, and 6 weeks postpartum (and during sexual risk periods during that time) / total woman-time on PrEP in active cohort = PrEP adherence rate (objective)	Lab analysis of TDF-DP measures	Quarterly
Secondary Outcomes			
Predictors of attrition at key steps in the PrEP cascade	Individual, pill/study and disease specific predictors of attrition	Study survey	Study survey: Every study visit
HIV outcomes	HIV testing data: HIV-uninfected, HIV-positive for mother and child (if mother seroconverts)	Electronic provider log (REDCap)	Every visit
Health outcomes and adverse events	Any side-effects, creatinine, any negative maternal or neonatal outcomes (for mother and infant)	Electronic provider log (REDCap)	During routine lab tests and visits

For **Aim 1**, each outcome will be described via cumulative incidences at fixed intervals (e.g., cumulative PrEP initiation by delivery) and incidence densities over time. The general statistical approaches to these outcomes are analogous; data will be described graphically, including product-limit graphs, with preliminary analyses based on standard approaches for rates and proportions. To address aims 1 and 2, the modelling approach will vary depending on the nature of the outcome. **PrEP initiation** will be modelled using a probit model (preferred to estimate risk factors for common outcomes) with individual-level covariates as fixed effects; when time-dependent or visit-specific covariates are included in the analysis of cumulative initiation (for **Aim 2**) we will shift to a mixed-effects setting with random effects around individual participants. **PrEP retention** will be examined using similar approaches; in addition, we will use time-to-event methods to estimate factors associated with time to loss (non-retention) among women having initiated PrEP. **PrEP adherence** will be modelled using mixed effects probit models as above and generalized estimating equations to examine the marginal effect of individual-level covariates on adherence during the study [85]. Throughout, robust estimates of standard errors will be used.

The same modelling approaches will be used to explore secondary implementation questions (**Aim 2**) such as the effect of individual, pill/study, and disease factors on PrEP initiation, retention and adherence outcomes (see Figure 1 for conceptual model). The main exposures include: **individual level factors**: risk perception, community/family support, sexual activity, risk, concerns about drug's side effects and harm on self

(pregnancy) and/or infant's health. **Pill regimen and study factors** include: PrEP side effects, time required to participate in study, patient-provider relationship measured from the participants' perspective. **Disease factors** include: stigma around HIV and PrEP, and partner's HIV status (see Table 5 for specific variables).

We will also describe the frequency of HIV outcomes, including maternal HIV acquisition and MTCT, and any laboratory or self-reported side effects (e.g. changes in creatinine or self-reported side-effects [GI symptoms, headache, and etc.]). Analyses will include pure-count and person-time approaches; for the latter, confidence intervals will be calculated following the method of Breslow and Day [86]. We will also describe infant outcomes over time (including birthweight, gestational age at delivery, pregnancy loss and any infant illness, hospitalization or death). While we expect the frequency of adverse HIV-related outcomes to be low, we will describe characteristics of women who did/did not acquire HIV, and consider further analyses using the approaches outlined above.

### Aim 3: Mathematical modeling considerations

The objective of **Aim 3** of the PrEP-PP study is to evaluate the potential impact of PrEP on prevention of HIV acquisition and perinatal transmission in South Africa. We will use the results from the cohort as parameters in the model to predict the impact of PrEP initiation, retention, and adherence on a national scale. This model will help identify the potential impact to identify priorities for HIV prevention strategies. We hypothesize that providing access and counseling on PrEP to HIV-negative pregnant and breastfeeding women will bring us closer to the virtual elimination of HIV acquisition and MTCT of HIV. The model will consider two-time points of HIV prevention (during pregnancy and breastfeeding) and two forms of MTCT of HIV: perinatal (at/before birth) and postnatal (through breastfeeding). The model will simulate maternal HIV acquisition during pregnancy and breastfeeding, and the associated risks of vertical transmission, as previously described [18]. The model that will be used in this analysis is the Thembisa model, a combined demographic and HIV model developed for SA [37]. The model divides the population into groups that are defined in terms of demographic characteristics (age and sex), sexual behavior (marital status and level of HIV risk behavior), level of engagement in HIV and HIV stage. The model has previously been calibrated to age-specific HIV prevalence data from SA antenatal surveys, as well as HIV prevalence data from household surveys and recorded death data. The method has been used to model the impact of different PMTCT of HIV strategies and to show the significant contribution of maternal seroconversion during pregnancy and breastfeeding to overall MTCT of HIV [18]. The model has also been used to consider the potential impact of PrEP if it is offered to high risk groups such as youth and commercial sex workers [38, 39], but has not previously been used to model the impact of PrEP during pregnancy and during the postnatal period. The model makes assumptions about the annual uptake of PrEP in different risk groups, the efficacy of PrEP in preventing HIV, the rate at which PrEP is discontinued, and the extent of condom migration in individuals who use PrEP. Using the outcomes of the cohort study to parameterize and validate the mathematical model, the model will estimate the number of HIV infections averted per 100 person-years of PrEP use.

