**Step 4:** *For participants on PrEP*, the study nurse performs a blood draw for creatinine clearance and a finger prick for DBS testing for adherence measures and (if applicable for this visit). See Table 1 for study calendar.

**Step 5 (for women on PrEP):** At each visit the study counselor will ask, and record responses, all participants on PrEP about any side effects associated with TDF/FTC, including diarrhea, nausea, fatigue, headache and rash (which are seen in about 10% of participants during the initiation of therapy). We will encourage participants to contact the study nurse if they experience side effects between visits.

**PrEP retention methods to improve adherence:** Each study visit will include counselling from peer counsellors who will discuss the importance of retention and adherence to PrEP for effectiveness. We will adapt messages from ongoing PrEP studies conducted by co-I [name] and team. We will also provide participants with a brochure to take home that discusses retention, adherence and side effects of PrEP. Each visit will include group and individual counselling. Group counselling will be led by a mother who has successfully taken PrEP for 3+ months to guide a discussion about the importance of retention, reminders on how to take the medication daily and how to address side-effects (e.g. nausea, headaches, etc).

**Step 6:** PrEP provision (for 1 or 2 months) and appointment reminder

*Follow-up & retention:* Tracing information will be taken at the enrolment visit and updated at each study visit. Retention activities will focus on scheduled measurement visits. Following our established approach in this

setting, we will provide reminder calls to participants before their measurement visits, and initiate tracing, including home visits, for women who do not attend the measurement visit within one week of the scheduled visit.

*PrEP provision:* monthly for the first 3 months, and then 2-months intervals after that. Participants on PrEP will have regular monitoring with laboratory tests, including creatinine levels to check for changes in renal function and dried blood spots (DBS) for adherence measures. Those with HBsAg+ will be excluded from the study. We will test for HIV seroconversion at every study visit.

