## **Compensation**

Participants will be given up to R250 in grocery vouchers for their time and effort in every study measurement visit as well as additional money to cover the cost of transport for each study visit. This is in line with ongoing research in the two sites, as the study visits will correspond to regular ANC or postpartum/well-baby clinical visits wherever possible. All participants will also receive refreshment on the day of their visit.

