#### ***Methods/Approach:***

- (1) Study flow figure (see Continuation Flowcharts)
- (2) Number screened per week and month (target= 18 per week, 72 per month) vs number enrolled
  - a. The projected sample size for the study is 1200 women enrolled until 12-months postpartum (estimated mean of 18-months follow-up).
- (3) Subjects initiating PrEP compared to those who do not
  - a. Estimated that 60% of women (n=720) will initiate PrEP during the study period (versus approximately 40% who will not).
- (4) Continuation and persistence by group
  - a. Assumed that approximately 75% of women on PrEP (n=540) will continue on PrEP at 12-months (defined as not missing >1 study visit among women on PrEP);
  - b. Assumed that 70% of those retained in care (n=378) will adhere to PrEP during at-risk periods.
- (5) Final completion rates
  - a. Compare final number of participants who enroll in study, who initiate PrEP, who are retained in care, and who adhere to PrEP to sample sizes needed to yield 80% power (i.e., n=1200, 720, 540, 378, respectively).
- (6) Number of subjects in analysis data sets
  - a. Consider number of participants that will potentially be excluded from analyses because of withdrawal from study, missing data on key covariates or outcomes, etc.

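### Aim 3 projects PrEP use from a supported cohort to national scale and validates the model on that same cohort, so a likely overstatement for routine care would go unseen

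*Combined protocol and SAP*

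**What the plan says.** The protocol's Aim 3 text (Section 6) says that the plan is to "use the results from the cohort as parameters in the model to predict the impact of PrEP initiation, retention, and adherence on a national scale". It then gives the cohort a double role, "Using the outcomes of the cohort study to parameterize and validate the mathematical model", and names one output: "the model will estimate the number of HIV infections averted per 100 person-years of PrEP use". It does not say which cohort outcomes set the model and which test it. Earlier calibration of the model is described for HIV prevalence and death data. No PrEP-use data are mentioned, and the text notes that the model is new to PrEP in pregnancy and the postnatal period. The SAP lists Aim 3 as an objective but has no analysis section for it.

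The inputs are defined and collected as follows.

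- **Initiation** (protocol Table 2): "of women who initiate PrEP over time / total # of women in active cohort".
- **Retention** (protocol Table 2): no more than one missed study visit among women prescribed PrEP. The SAP's study measures and its Table 1 repeat this under the name continuation. The SAP's objectives also give a refill-based definition within 45 days of starting.
- **Support**: participants receive "up to R250 in grocery vouchers for their time and effort in every study measurement visit" (Compensation) plus transport costs. Under Follow-up & retention, staff make reminder calls and "initiate tracing, including home visits, for women who do not attend the measurement visit within one week of the scheduled visit". PrEP users also get group counselling led by a peer.
- **Enrolment**: consecutive eligible, consenting women, who may join without agreeing to take PrEP.
- **Screening**: SAP 2.2 tracks "Number screened per week and month (target= 18 per week, 72 per month) vs number enrolled", and the SAP's monthly report template has rows for screened, ineligible and refusing women.

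**The concern.** Two features combine. First, the retention input counts attendance at study visits, which is exactly what payment, reminders and tracing are meant to raise. Nothing in the documents says that national routine care provides these. Second, the data that set the model also test it, so the test is run among the same supported women and cannot show whether their values hold elsewhere.

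Aim 3 is meant to guide prevention priorities. If the inputs run high for routine care, projected national coverage and total infections averted run high too. If the improved cascade is set as a fixed target, an inflated starting point also makes the gain from improvement look smaller. A reported validation would give readers confidence on a question that it did not address.

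**Working it through.** **Step 1. The plan's own cascade.** Inputs from the sample size sections and SAP 2.2: N = 1200, initiation 60%, retention 75%, adherence 70%.

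1200 × 0.60 = 720; 720 × 0.75 = 540; 540 × 0.70 = 378. These match the SAP's 720, 540 and 378. Effective coverage of the cohort is 378/1200 = 31.5%.

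**Step 2. What a check on the same cohort can show.**

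- If the cascade outcomes are what is checked, the model is compared with the values it was given, so agreement says little.
- If HIV infections in the cohort are checked, with only the cascade as input, the check tests the model's structure. Predicted and observed infections still come from the same supported women. A gap between cohort and routine care enters neither side.

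The text does not say which is meant. On either reading, transfer to routine care is not tested.

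**Step 3. Effect of study support.** Let routine values be a fraction f of cohort values (f is assumed).

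- Initiation and retention reduced: coverage = 0.315 × f². At f = 0.9, 0.315 × 0.81 = 25.5%. At f = 0.75, 0.315 × 0.5625 = 17.7%. The cohort value is 1.23 or 1.78 times too high.
- Adherence reduced as well: coverage = 0.315 × f³, which gives 23.0% or 13.3%.

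**Step 4. Effect of consent selection.** Let e be the share of women who enrol, and k the initiation rate of non-enrollees relative to enrollees (both assumed). Relative overstatement of uptake = 1/(e + (1 − e)k) − 1.

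| e | k = 1 | k = 0.5 | k = 0 |
|---|---|---|---|
| 0.9 | 0% | 5% | 11% |
| 0.7 | 0% | 18% | 43% |
| 0.5 | 0% | 33% | 100% |

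**Step 5. The named output.** For illustration, take incidence 10.7 per 100 person-years and relative risk 0.57 in women (both from the protocol's Background), a mean follow-up of 1.5 years, and a simple proportional calculation without onward transmission.

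- Uptake 60%: 1200 × 1.5 × 0.60 = 1080 person-years on PrEP; averted 1080 × 0.107 × 0.43 = 49.7; per 100 person-years 4.60.
- Uptake 30%: 540 person-years; averted 24.85; per 100 person-years again 4.60.
- Protective adherence halved, with protection assumed proportional to it: 4.60 × 0.5 = 2.30.

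Uptake cancels in this ratio, but adherence does not. National totals depend on both.

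**Step 6. Precision of a check on HIV incidence.** With the same inputs, 1800 × 0.107 = 193 infections without PrEP. At 60% uptake, 192.6 × (1 − 0.60 × 0.43) = 143. An exact Poisson 95% interval at 143 events is about 0.84 to 1.18 times the observed count. The analysis section expects adverse HIV-related outcomes to be infrequent, so the real count may be far lower and the interval wider.

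**The case against.** The case on the other side has real weight.

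- **Selection on willingness to take PrEP is limited.** Enrolment is consecutive, women who do not want PrEP may join, and they are followed. This stands. The k = 0 column in Step 4 is a worst case, and study support is the stronger ground.
- **The named output barely responds to uptake.** This also stands. An initiation error affects national totals, not infections averted per 100 person-years of use.
- **Validation may mean checking HIV incidence.** The cohort's outcomes include maternal and infant HIV, so the text allows a design that sets cascade inputs and tests infections. A reader might infer that the model must pass its check by construction. The documents do not support that; it follows only if cascade outcomes are what is checked. The defect is that the plan does not say.
- **There is no routine-care comparator.** A reader might infer that coverage is overstated as a matter of fact. The documents hold no figure to show it. Aim 3 speaks of potential impact, and the time that participation takes is itself listed as a factor affecting the cascade, so some effects could run the other way.
- **The SAP already plans censoring weights, multiple imputation and a baseline comparison.** The first two deal with losses inside the cohort. The comparison covers baseline characteristics against Cape Town women, not PrEP use nationally.

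Two features of the plan support an upward direction. The initiation and retention denominators use the active cohort, while women who move, transfer or are lost are censored. The sample size sections also base the analysis on women who complete 12 months postpartum.

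**Conclusion.** The point holds as a cheap improvement. Aim 3 projects values from a paid, reminded and traced cohort to the country and plans no routine-care scenario, external PrEP-use data or held-back outcome. Coverage and total infections averted are likely overstated for routine care, by an unknown amount, and a check within the cohort cannot reveal it.

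The illustrations rest on assumed values. Routine initiation and retention at 90% or 75% of the cohort's would take 31.5% coverage to 25.5% or 17.7%. Consent selection adds anything from nothing to 11%, 43% or 100% at enrolment shares of 0.9, 0.7 and 0.5. The documents support neither end of that range over the other, though open enrolment argues against the top. The per-person-year output is exposed mainly through adherence.

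**What to change.** 1. **Separate inputs from the check.** State that cascade values are the model inputs and that cohort HIV incidence, not used as an input, is the internal check: predicted against observed, with an exact Poisson interval. Otherwise call the step calibration and drop the word validate. In either case, state that the check does not test transfer to routine care.
2. **Add lower scenarios; this is the essential part.** For the national projection, label cohort retention and adherence as the supported-care upper scenario. Pre-specify lower scenarios for initiation, discontinuation and adherence.
3. **Bound initiation.** Report initiators over enrolled women, and initiators over enrolled women plus eligible refusals, using the screening counts in the SAP's monthly report. Split ineligible women by reason, since some exclusions are themselves reasons not to offer PrEP. Note that women who decline before screening may be missed.

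The cost is a paragraph of text, a few extra model runs and a split of the ineligible count by reason. Nothing changes for participants. The drawback is a wider and less favourable headline range.
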